03 APRIL 2018

Date

SYNOPSIS

NAME OF COMPANY: Achieve Life Sciences, Inc
NAME OF INVESTIGATIONAL MEDICINAL PRODUCT (CYTISINE): Cytisine 1.5 mg film-coated tablet
TITLE OF STUDY: A phase 1 open label, randomized, two-way crossover study in healthy smokers to investigate the effect of food on the bioavailability of cytisine in a new formulation
PRINCIPAL INVESTIGATOR: [REDACTED]
STUDY CENTRE: Simbec Research Ltd (Simbec) [name]
CLINICAL PHASE: I
OBJECTIVES: Primary: 
• To compare the bioavailability (C_{max} and $AUC_{0-\infty}$) of cytisine in healthy smokers under fed and fasted conditions, following administration of 3 mg cytisine (2 x 1.5 mg cytisine tablets).• To assess the extent of renal elimination of cytisine via measurement of urinary concentrations, following administration of 3 mg cytisine (2 x 1.5 mg cytisine tablets). Secondary: 
• To compare the AUC_{0-t}, $T_{1/2}$ and T_{max} of cytisine in subjects under fed and fasted conditions, following administration of 3 mg cytisine (2 x 1.5 mg cytisine tablets).• To assess the safety and tolerability of cytisine in a new formulation at the 3 mg dose level under fed and fasted conditions.
METHODOLOGY: 
This will be an open-label, randomised, 2- treatment period, single-dose crossover study to determine the comparative bioavailability and renal elimination of cytisine following single-dose administration in healthy smokers under fed and fasted conditions.
 
The study will be comprised of a pre-study screen, followed by 2 treatment periods (1 and 2) and a post-study follow-up.
 
Screening (Day -28 to Day -1): Screening assessments will be carried out within 28 days before first administration of cytisine.
 
Baseline (Day 0): Baseline assessments will be carried out one day before the first administration of cytisine.
 
Treatment Periods (Day 1 to Day 5): Eligible subjects will receive a single-dose of cytisine under fed and fasted conditions during 2 treatment periods over a 5-day time frame. Each treatment period will be approximately 2 days' duration in which blood and urine samples will be collected over a 48 h period post cytisine dosing. This will require a total of 5 overnight stays in the Clinical Unit. The study will begin the afternoon before the first dosing on Day 0 and the treatment period will start with the first dose on Day 1 and continue until 48 hours (h) after the second dosing on Day 5.
 
Subjects will arrive at the Clinical Unit on Day 0 and will undergo an overnight fast of at least

10 h prior to first dosing on Day 1. Randomisation will occur on the morning of Day 1, Period 1, and cytisine will be administered under fasted (after an overnight fast of at least 10 h) or fed (after a high fat breakfast) conditions. Subjects will complete all 48 h postdose assessments prior to starting Period 2 and the second dosing on Day 3.

Plasma and urine samples will be collected predose and up to 48 h postdose during each period (18 plasma samples and 11 urine samples per period) for the measurement of plasma and urinary cytisine concentrations. The 2 periods allow 48 hours between dose administrations. Safety will also be evaluated at specified times.

Post Study: Post study telephone follow-up will be conducted 6 to 8 days after the second dose of cytisine.

NUMBER OF SUBJECTS: 12 subjects will be randomised/enrolled to complete the study.

MAIN INCLUSION CRITERIA:

Healthy smokers (males or females who are non-pregnant/non-lactating) aged 18 - 55 years, with no allergy or sensitivity to cytisine or any of its excipients, who unless surgically sterile, abstaining from sexual intercourse or of non-child bearing potential, are willing to use an effective method of contraception from the first dose and for 3 months after the last dose of cytisine.

CYTISINE ADMINISTRATION:

Each subject will receive cytisine over 2 treatment periods under fed and fasted conditions in accordance with the randomisation schedule:

Schedule A (6 subjects):

- Period 1: Cytisine (2 x 1.5 mg tablets) will be administered 30 minutes after the start of a high fat breakfast (fed state).
- Period 2: Cytisine (2 x 1.5 mg tablets) will be administered after an overnight fast of at least 10 hours (fasting state).

Schedule B (6 subjects):

- Period 1: Cytisine (2 x 1.5 mg tablets) will be administered after an overnight fast of at least 10 hours (fasting state).
- Period 2: Cytisine (2 x 1.5 mg tablets) will be administered 30 minutes after the start of a high fat breakfast (fed state).

240 mL water will be given with the dose.

CRITERIA FOR EVALUATION:

Study Endpoints:

Plasma: The following PK endpoints will be derived from plasma cytisine concentration versus time data following administration of 3 mg cytisine (2 x 1.5 mg) under fed and fasted conditions: Maximum concentration (C_{max}), time to C_{max} (T_{max}), elimination rate constant (k_{el}), terminal elimination half-life ($T_{1/2}$), area under the concentration versus time curve (AUC) from time of dosing to last measurable concentration (AUC_{0t}), AUC extrapolated to infinity (AUC_{0inf}) and $AUC_{\% \text{ extrapolated}}$ (residual area).

Urine: Amount excreted in urine over time (A_e) and percent of cytisine excreted in urine ($A_e\%$) will be calculated.

Safety Endpoints: AEs, vital signs (supine systolic/diastolic pressure, pulse and oral temperature), 12 lead ECG, laboratory safety (haematology, biochemistry and urinalysis).

STATISTICAL METHODS:

All statistical analysis will be performed using SAS[®] version 9.3.

Demographic and Background Data: All demographic and background data will be listed. Demographic data will be summarised (age, height, weight, BMI and race) by gender and overall. Subject disposition and analysis sets (safety, PK) will also be listed and summarised by frequency.

Urine Excretion and PK: All plasma and urine cytisine concentrations and derived PK data following administration of cytisine will be listed and the data summarised descriptively.

Individual and mean plasma concentration time curves will also be plotted. In order to compare fed vs fasted conditions, following logarithmic transformation, C_{max} , $AUC_{0-\infty}$, AUC_{0-t} and total Ae values will be subjected to an analysis of variance (ANOVA). Point estimates and 90% confidence intervals (CI) will be constructed for the contrast between the two conditions. A comparison of T_{max} will be performed using the Wilcoxon Signed-Rank test. In addition, the Hodges-Lehmann estimate of the median difference in T_{max} and 95% confidence interval will be presented.

Safety: All safety data will be listed.

AEs will be coded using Medical Dictionary for Regulatory Activities (MedDRA) version 20.0 or higher. The incidence of treatment emergent AEs (TEAE) will be summarised by organ system, preferred term, severity and relationship to study drug. Abnormal laboratory safety results will be listed separately.

DURATION OF STUDY:	Approximately 6 weeks for each individual (from screening to post-study follow-up).
---------------------------	---

TABLE OF CONTENTS

SYNOPSIS	3
LIST OF ABBREVIATIONS AND DEFINITIONS OF TERMS.....	11
1. ETHICS	12
1.1. Research Ethics Committee.....	12
1.2. Subject Information and Consent	12
1.3. Indemnity Arrangements	13
2. INTRODUCTION AND BACKGROUND	13
2.1. Smoking and Health	13
2.2. Cytisine	13
3. RATIONALE FOR THE STUDY.....	15
4. STUDY OBJECTIVES	15
4.1. Primary Objective.....	15
4.2. Secondary Objectives	15
5. INVESTIGATIONAL PLAN.....	15
5.1. Study Design.....	15
5.2. Discussion of Study Design.....	17
6. SELECTION OF STUDY POPULATION	17
6.1. Inclusion Criteria	17
6.1.1. To be Confirmed at Screening.....	17
6.1.2. To be Re-Confirmed Prior to Dosing	18
6.2. Exclusion Criteria	19
6.2.1. To be Confirmed at Screening.....	19
6.2.2. To be Re-Confirmed Prior to Dosing:	19
6.3. Removal of Subjects from Therapy or Assessment.....	19
7. RESTRICTIONS PRIOR AND DURING THE STUDY	20
7.1. Confinement	20
7.2. Diet and Fluid Restrictions	20
7.2.1. Meal Times	20
7.2.2. Fluid Intake.....	21
7.2.3. Smoking.....	21
7.2.4. Alcohol Intake	21

7.2.5.	Caffeine.....	22
7.2.6.	Poppy and Sesame Seeds.....	22
7.2.7.	Grapefruit Juice and Other Restrictions	22
7.3.	Other Life-Style Restrictions.....	22
7.3.1.	Strenuous Exercise.....	22

ULOQ	Upper Limit of Quantification
WBC	White Blood Cell Count
λ _z	Apparent Terminal Elimination Rate Constant

1. ETHICS

1.1. Research Ethics Committee

This study protocol will be submitted to the Research Ethics Committee (REC) for review and approval. The approval of the REC must be obtained before commencement of any study procedures.

The favourable opinion is conditional upon the Sponsor registering the clinical trial in a publicly accessible database, within 6 weeks of the first participant recruited.

All substantial protocol amendments must be approved by the REC responsible for the study. Non-substantial amendments will not require prior approval by the REC.

If the study is stopped due to adverse events (AEs), it will not be recommenced without reference to the REC responsible for the study.

The outcome of the study (e.g. completed) will be reported to the REC responsible for the study within 90 days of completion of the last subject's final study procedures. In the event of the study being prematurely terminated, a summary safety report will be submitted to the REC responsible for the study within 15 days.

A summary of the clinical study report will be submitted to the REC responsible for the study within 1 year of completion of the last subject's final study procedures.

The REC will be informed that [REDACTED] is a commercial organisation and that the study is funded by Achieve Life Science. The subjects who take part in the clinical study will be paid for their inconvenience and have been informed that there will be no benefits gained by their participation. All potential conflicts of interest will be declared by the Investigators.

1.2. Subject Information and Consent

Potential subjects who volunteer for participation in the study will be informed of the aims, methods, anticipated benefits and potential hazards of the study and any possible discomfort it may entail. Information will be given in both oral and written form and in the manner deemed appropriate by the Clinical Unit standard operating procedures (SOPs). Each subject will also be informed of his/her right to withdraw from the study at any time, for any reason.

A written explanation (participant information sheet) and informed consent form will be provided and the subject will be allowed sufficient time to consider the study information. Prior to signing the informed consent form, the subject will be given an opportunity to discuss any issues concerning the study with an Investigator who has suitable knowledge of the study and will have all questions answered openly and honestly.

If the subject is willing to participate in the study, the informed consent form will be signed and personally dated by the subject and the person taking consent. The subject will receive a copy of the informed consent form together with the participant information sheet and the original signed informed consent form will be retained with the study records at the Investigator site. In addition, the actions and completion of the consenting process will be recorded in the subject's medical record (i.e., source document).

1.3. Indemnity Arrangements

The Sponsor and [REDACTED] carry insurance to pay compensation for injury, accident, ill health or death caused by participation in this study without regard to proof of negligence in accordance with the insurance and compensation in the event of injury in phase I clinical trials 2012, guidance issued by the ABPI, the BioIndustry Association and the Clinical Contract Research Association in consultation with the Department of Health and the National Research Ethics Service.

2. INTRODUCTION AND BACKGROUND

2.1. Smoking and Health

Tobacco smoking contributes to some 5 million premature deaths each year worldwide.¹ Smoking is highly addictive, with more than 95% of unaided attempts at cessation failing to last 6 months.² Every year that a smoker delays quitting beyond the mid-30s, it has been estimated that the person loses 3 months of life expectancy.³ The World Health Organization's Framework Convention on Tobacco Control identifies evidence-based approaches to promote smoking cessation, which include mass-media campaigns, tax increases on tobacco, and help for smokers wanting to stop.⁴

2.2. Cytisine

[REDACTED] containing the active substance cytisine has been licensed and marketed in Central and Eastern Europe for several decades by [REDACTED], but remains relatively unknown outside Eastern Europe despite requests for market licensing worldwide.⁵⁻⁷

Cytisine's mechanism of action has assisted basic pharmacologists in understanding the complex pharmacology of the various subtypes of the nicotinic acetylcholine receptor.⁸ These studies have shown that both nicotine and cytisine bind strongly and preferentially to pre-synaptic $\alpha_4\beta_2$ receptors^{9,10} that mediate the release of dopamine in the shell of the *nucleus accumbens*. This receptor subtype has been implicated in the development and maintenance of nicotine dependence¹¹ and was the primary target for the drug varenicline, which has proved effective in aiding smoking cessation.¹²

Three studies have evaluated the pharmacokinetics of cytisine in man.

Study CYT-BIO-02-07 was conducted according to the principles of Good Clinical Practice (GCP) and sponsored by [REDACTED]. The pharmacokinetic profile of cytisine in plasma was determined following administration of 1.5 mg cytisine (in the form of a [REDACTED] tablet) in 36 male healthy non-smoking volunteers. All drug administrations were given in the fasted state. The primary PK outcomes are summarised in (Table 1):

Table 1: CYT-BIO-02-07 PK Results

C_{\max}	15.55 ng/mL
AUC_{0-t}	59.80 ng.h/mL
$AUC_{0-\infty}$	73.63 ng.h/mL
T_{\max}	0.92 h (\approx 55 min)
$T_{1/2}$	4.09 h

Cummulative cytisine levels excreted in the urine during the 24 hours post administration period indicated that approximately 64% of administered dose was excreted as parent compound (34.71% - 100.24%).

A second study¹³ reported the pharmacokinetic profile of cytisine in seven healthy subjects (aged between 20 and 39 years) following administration of 3 mg cytisine . Subjects were eligible if they were current cigarette smokers at the time of the study and on average, the subjects smoked 10.6 cigarettes per day. There was no restriction on diet or smoking during the study. The primary PK outcomes are summarised in (Table 2):

Table 2: Single Dose PK Results

C_{\max}	27.76 ng/mL
$T_{1/2}$	4.8 h
T_{\max}	1-2 h
VD	115 L
CL	16.7 L/h

Cummulative urinary excretion was not evaluated; however, cytisine was still detectable in the urine collected at 24 h for all subjects (mean concentration at 24 hr was 428.15 ng/mL).

A third study (ACH-CYT-01) examined the pharmacokinetic profile of cytisine in healthy non-smoking subjects following administration of 3 mg cytisine in the original marketed formulation during the fed and fasted states. The primary PK outcomes are summarized in (Table 3):

Table 3: ACH-CYT-01 PK Results

	Fasted	Fed
C_{\max}	22.9 ng/mL	22.3 ng/mL
AUC_{0-t}	166 ng.h/mL	160 ng.h/mL
$AUC_{0-\infty}$	173 ng.h/mL	168 ng.h/mL
T_{\max}	0.75 h	2.75 h
$T_{1/2}$	4.59 h	4.77 h

Fasted subjects received a single dose of 3 mg cytisine and approximately 82% of the dose was recovered from urine within 24 hours. Final urinary concentrations in the study were measured in the 12-24 hour epoch and were non-zero for all subjects, indicating that renal excretion was still ongoing beyond 24 hours after cytisine administration. However, based on the diminishing urinary concentrations over time, it can be concluded that excretion is likely to be complete within 48 hours.

3. RATIONALE FOR THE STUDY

In the recent bioavailability study evaluating the original marketed formulation for cytisine, no food effect was observed for $AUC_{0-\infty}$ (or AUC_{0-t}) with values considered bioequivalent as the 90% CI for the difference between fed and fasted states fell within the range 80 -125%. Consistent with this, the amounts of cytisine recovered from urine within 24 h were similar between fed and fasted states, despite C_{max} being lower in the fed state. In that study, it was concluded that there was no clinically significant food effect for cytisine and there were no safety concerns following administration of a single dose of 3 mg cytisine under fed or fasted conditions for healthy non-smokers.

A revised formulation has been subsequently developed, eliminating lactose and introducing lower formic acid containing-excipients, to retard the formation of the breakdown substance *N*-formylcytisine. Initial studies indicate that the revised formulation has improved stability at 24 months and that the shelf-life could be extended to 36 months based on the preliminary stability information. This study will evaluate if there is any food effect for cytisine using this new formulation in healthy smokers.

4. STUDY OBJECTIVES

4.1. Primary Objective

1. To compare the bioavailability (C_{max} and $AUC_{0-\infty}$) of cytisine in smokers under fed and fasted conditions, following administration of 3 mg cytisine (2 x 1.5 mg cytisine tablets).
2. To assess the extent of renal elimination (A_e and $A_e\%$) of cytisine via measurement of urinary concentrations, following administration of 3 mg cytisine (2 x 1.5 mg cytisine tablets).

4.2. Secondary Objectives

[figure not shown]
1. To compare the AUC_{0-t} , $T_{1/2}$ and T_{max} of cytisine in subjects under fed and fasted conditions, following administration of 3 mg cytisine (2 x 1.5 mg cytisine tablets).
2. To assess the safety and tolerability of cytisine in a new formulation at the 3 mg dose level under fed and fasted conditions.

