Individual pharmacokinetic parameters and descriptive statistics for the pharmacokinetic parameters obtained for each treatment will be presented. If no reliable pharmacokinetic parameter could be determined for more than 1/3 of the subjects, only the minimum and maximum values will be presented for that parameter and all other descriptive statistics will be omitted. Missing pharmacokinetic parameter data will not be imputed.

Urine: The urine PK parameters amount excreted in urine over time (A_e) and percent of drug excreted in urine ($A_e\%$) will be derived from the urine concentration-time data for all subjects in the safety analysis set. Derived urine PK parameters will be listed and summarised by treatment.

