15.7. Pharmacokinetic Analysis

Following logarithmic transformation, C_{max} , AUC_{0-t} , $AUC_{0-\infty}$ and Total A_e values will be subjected to an analysis of variance (ANOVA) including fixed effects for sequence, period, treatment and subject nested within sequence. Point estimates and 90% confidence intervals (CI) will be constructed for the contrasts between fed and fasted states using the residual mean square error obtained from the ANOVA. The point and interval estimates will be back-transformed to give estimates of the ratios of the geometric least squares means (LSmean) and corresponding 90% CI. In addition, estimated geometric means will be presented.

A comparison of T_{max} will be performed using the Wilcoxon Signed-Rank test. In addition, the Hodges-Lehmann estimate of the median difference in T_{max} and 95% CI will be presented.

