### 4.2 SECONDARY VARIABLES

The secondary plasma cytosine pharmacokinetic endpoints for this study are as follows:

- $T_{max}$  Time of occurrence of maximum observed plasma concentration.
- $AUC_{0-t}$  AUC from the time of zero to the last sampling time at which concentrations were at or above the lower limit of quantification (LLOQ), calculated by the linear-up/log-down trapezoidal rule.
- %AUC Residual area or percentage of extrapolated part for the calculation of  $AUC_{0-\infty}$ , calculated as  $100*[1-(AUC_{0-t}/AUC_{0-\infty})]$ .
- $\lambda_z$  Apparent terminal elimination rate constant.
- $t_{1/2}$  Apparent terminal elimination half-life, calculated from  $\ln 2/\lambda_z$ .
- $CL/F$  Apparent total body clearance.
- $Vd/F$  Apparent volume of distribution.

The safety endpoints for this study are as follows:

- Adverse events (AEs).
- Laboratory safety data (biochemistry, haematology, urinalysis and microscopy).
- Vital signs (supine systolic/diastolic blood pressure, pulse rate and oral temperature).
- 12-lead ECG (heart rate, PR interval, QRS width, QT interval and QT interval corrected using Fridericia's formula (QTcF interval)).

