The terminal elimination rate constant ( $\lambda_z$ ) will be determined by plotting the concentration data versus time on a semi-logarithmic scale. The parameter will be estimated by linear least square regression analysis, using the last three (or more) non-zero concentrations. The upper and the lower time points, as well as the number of time points, used for  $\lambda_z$  estimation will be reported. Values of  $\lambda_z$ ,  $AUC_{0-\infty}$ , %AUC and  $t_{1/2}$  will not be reported for cases where  $\lambda_z$  cannot be reliably determined.

$AUC_{0-t}$  will be calculated using the linear-up/log-down trapezoidal method.

For the calculation of derived pharmacokinetic parameters, concentrations below the limit of quantification (BLQ) will be assigned a value of zero. In case of a deviation from the theoretical time, the actual time of blood sample will be used in the calculation of the derived pharmacokinetic parameters. Should the actual time be unavailable but a blood sample was taken, the nominal time point will be assigned.

Derived pharmacokinetic parameters will be listed and summarised for each treatment. The descriptive statistics presented will be N, n, arithmetic mean, arithmetic standard deviation (SD), coefficient of variation (CV%), minimum, median, maximum and geometric mean (with the exception of  $T_{max}$ ).

If no reliable PK parameter can be determined for more than a third of the subjects, only n, minimum and maximum values will be presented for that parameter and all other descriptive statistics will be omitted.

Plasma PK parameter data listings will be presented using the Safety Set. Plasma PK data summaries will be presented using the PK Set and also the Safety Set if they differ. All PK parameter data included in listings and summaries will be presented to three significant figures with the exception of the CV% which will be presented to one decimal place.

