#### 11.4.2.1 Statistical Analysis of Plasma PK Parameters

Following logarithmic transformation,  $C_{max}$ ,  $AUC_{0-t}$ , and  $AUC_{0-\infty}$  values will be subjected to an analysis of variance (ANOVA) including fixed effects for sequence (treatment schedule), period, treatment and subject nested within sequence. Point estimates and 90% confidence intervals (CI) will be constructed for the contrasts between fed and fasted states using the residual mean square error obtained from the ANOVA. The point and interval estimates will be back-transformed to give estimates of the ratios of the geometric least squares means (LSmean) and corresponding 90% CI. In addition, estimated geometric means will be presented.

A comparison of  $T_{max}$  will be performed using the Wilcoxon Signed-Rank test. In addition, the Hodges-Lehmann estimate of the median difference in  $T_{max}$  and 95% CI will be presented.

The statistical analysis of the plasma PK parameters will be performed using the PK Set and also the Safety Set if they differ. Geometric LSmeans will be presented to three significant figures and the ratios and 90% CIs will be presented to 2 decimal places.

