### 14.4.2 Derived Pharmacokinetic Data

Table 14.4.2.1	Summary of Derived Plasma Cytisine Pharmacokinetic Parameters	PK Set
Table 14.4.2.2	Summary of Derived Urine Cytisine Pharmacokinetic Parameters	Urine Excretion Set
Table 14.4.2.3	Summary of Statistical Analysis of Cytisine $C_{max}$ and AUC	PK Set
Table 14.4.2.4	Summary of Statistical Analysis of Cytisine $T_{max}$	PK Set
Table 14.4.2.5	Summary of Statistical Analysis of Cytisine Total Amount Excreted in Urine	Urine Excretion Set
Table 14.4.2.6	Summary of Derived Plasma Cytisine Pharmacokinetic Parameters – (if required)	Safety Set
Table 14.4.2.7	Summary of Derived Urine Cytisine Pharmacokinetic Parameters – (if required)	Safety Set
Table 14.4.2.8	Summary of Statistical Analysis of Cytisine $C_{max}$ and AUC – (if required)	Safety Set
Table 14.4.2.9	Summary of Statistical Analysis of Cytisine $T_{max}$ – (if required)	Safety Set

Table 14.4.2.10 Summary of Statistical Analysis of Cytisine Total Amount Excreted in Urine – (if required) Safety Set

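### T1/2 is named for fed/fasted comparison in secondary objective 1 but, unlike AUC0-t and Tmax, has no planned contrast or confidence interval

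*Protocol*

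**What the plan says.** The protocol (synopsis and 4.2) and SAP section 2 set the same secondary objective 1: "To compare the AUC_{0-t} , $T_{1/2}$ and T_{max} of cytisine in subjects under fed and fasted conditions", after a 3 mg dose. The planned handling of the three parameters is as follows.

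- **AUC0-t.** It is log-transformed with Cmax and AUC0-∞ (and total Ae) and analysed in the crossover model: "values will be subjected to an analysis of variance (ANOVA) including fixed effects for sequence, period, treatment and subject nested within sequence" (protocol 15.7). SAP 11.4.2.1 has the same model for Cmax and the two AUCs: "values will be subjected to an analysis of variance (ANOVA) including fixed effects for sequence (treatment schedule), period, treatment and subject nested within sequence". The output is a fed/fasted geometric mean ratio with a 90% CI.
- **Tmax.** It gets a Wilcoxon signed-rank test and a Hodges-Lehmann estimate with a 95% CI (same sections).
- **T1/2.** It is derived for each profile, then handled descriptively. Protocol 15.6: "Individual pharmacokinetic parameters and descriptive statistics for the pharmacokinetic parameters obtained for each treatment will be presented". SAP 11.4.2: "Derived pharmacokinetic parameters will be listed and summarised for each treatment". The SAP summary includes the geometric mean, and individual values appear in Listing 16.2.5.3.

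The six statistical-analysis tables in SAP 14.4.2 (14.4.2.3 to 14.4.2.5, and 14.4.2.8 to 14.4.2.10 if required) cover Cmax and AUC, Tmax, and total Ae. The title of Table 14.4.2.3 is "Summary of Statistical Analysis of Cytisine $C_{max}$ and AUC"; no title names T1/2. SAP 1.2 records no decision to leave T1/2 descriptive.

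**The concern.** The objective puts T1/2 beside AUC0-t and Tmax under one verb, and the plan's own way of comparing is a contrast with an interval. The synopsis opens the ANOVA description with "In order to compare fed vs fasted conditions, following logarithmic transformation". Of the seven parameters that SAP 4.2 lists as secondary plasma endpoints, the objective names three for comparison, and T1/2 is the only one of those three without a contrast.

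Protocol 5.2 justifies the crossover by the precision gained when each subject is his own control. Separate fed and fasted summaries do not use that pairing, because their SD and CV% contain the between-subject variation that the design is meant to remove. A reader could see two half-lives and their spread, but could not tell from the tables whether the data exclude, say, a 10% or a 25% change with food.

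**Working it through.** **Coverage of the objective.** AUC0-t: contrast and CI planned. Tmax: contrast and CI planned. T1/2: neither. That is two of three. The methods text and table list are legible and enough to show this; the redacted table shells are not counted either way.

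**The plan's own figure.** Protocol 15.4 says 4 subjects suffice for AUC0-∞ (CV 6%, true ratio 1, 80% power, alpha 5%). Two one-sided tests at 5% each with limits 0.80–1.25 in a 2×2 crossover give a power of 0.888 at N = 4, so the figure reproduces. At N = 12 the power is about 1.00. T1/2 plays no part in this calculation.

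**What a T1/2 interval would show.** Inputs:

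- 12 subjects, 6 per sequence (protocol 15.4, SAP 3.5).
- Prior-study T1/2 of 4.59 h fasted and 4.77 h fed (protocol Table 3), so the ratio is 4.77/4.59 = 1.0392.
- Within-subject CV of T1/2: not in the documents, so a range is assumed. The values 6% and 23% are those given for AUC0-∞ and Cmax (protocol 15.4).

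Formulas:

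- s = √ln(1 + CV²)
- SE = s·√[0.5·(1/nA + 1/nB)], with df = nA + nB − 2
- 90% CI = ratio ÷ and × exp(t0.95,df · SE)

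For 6 + 6 pairs, t = 1.8125 on 10 df. At CV 6%, s = √ln(1.0036) = 0.0599, SE = 0.0599 × 0.4082 = 0.0245, and the factor is exp(1.8125 × 0.0245) = 1.045. For 6 + 5 pairs, t = 1.8331 on 9 df. Fed hours are 4.77 ÷ and × the 12-pair factor, which treats the fasted value as 4.59 h.

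| Assumed CV | Factor, 12 pairs | Factor, 11 pairs | 90% CI around 1.039 (12 pairs) | Fed T1/2 (h) |
|---|---|---|---|---|
| 6% | 1.045 | 1.048 | 0.994–1.086 | 4.56–4.99 |
| 10% | 1.077 | 1.081 | 0.965–1.119 | 4.43–5.14 |
| 20% | 1.158 | 1.168 | 0.898–1.203 | 4.12–5.52 |
| 23% | 1.183 | 1.195 | 0.879–1.229 | 4.03–5.64 |
| 30% | 1.243 | 1.259 | 0.836–1.291 | 3.84–5.93 |

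**When the interval would exclude 1.** At a ratio of 1.0392 this needs 1.8125 × 0.4082 × s < ln(1.0392) = 0.0385, so s < 0.0520 and CV below about 5.2%. The interval's use is to show which larger changes are ruled out, not to resolve a 4% difference.

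**Incomplete pairs.** T1/2 is not reported when λz is unreliable (protocol 15.6, SAP 11.4.2), so pairs may be lost. With subject as a fixed effect, a subject with one value adds nothing to the treatment contrast. In one simulated data set of 12 subjects, with one value deleted from each of two, the model gave the same treatment estimate (0.06353) and SE (0.01979) on all 22 values as on the 20 values from the 10 complete pairs. Residual df also agree: 22 − 12 − 1 − 1 = 8 and 20 − 10 − 1 − 1 = 8.

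**The case against.** The case for leaving the plan alone has four parts.

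1. **To compare need not mean to test or to give an interval.** The documents say this is not a formal bioequivalence comparison, the handling of T1/2 is unambiguous, and protocol and SAP agree. This is fair, and it is why the point is minor. But the same objective leads to intervals for the other two parameters, and nothing says that T1/2 was meant to differ.
2. **The point estimate can almost be read off.** The ANOVA estimate is the average of the two sequence-mean differences in ln(T1/2). With 6 complete pairs per sequence this equals the overall mean difference, so its exponent is the fed geometric mean over the fasted one, and both are planned in Table 14.4.2.1. That is correct, apart from rounding to three significant figures. What is missing in that case is the interval, which a reader would have to compute from the listing. If pairs are lost unequally between sequences, the ratio of the two summaries no longer equals the model estimate.
3. **The illustration is soft.** The CVs are assumed. Table 3 does not say what kind of average it shows, and its fasted Cmax (22.9 ng/mL) differs from the 29.8 ng/mL in protocol 15.4. The earlier study used another formulation in non-smokers. All of this stands; it limits the numbers, not the existence of the gap.
4. **The one-third rule.** If T1/2 is unreliable in more than a third of subjects, most descriptive statistics are dropped, and it could look odd to print a ratio beside them. That rule governs descriptive statistics and already sits beside the AUC0-∞ ANOVA in the same way, so it is no reason against adding T1/2.

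**Conclusion.** The point holds as a minor gap between objective and analysis, present in both documents. One of the three parameters that secondary objective 1 names for comparison has no planned fed/fasted contrast or interval. An informal comparison remains possible from the planned summaries and listing. The documents set no T1/2 margin and tie no decision to it.

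The omitted interval would have a 90% factor between 1.045 and 1.243 with 12 complete pairs. This rests on an assumed within-subject CV of 6% to 30% and on the usual log-normal crossover model. The omission itself rests on no assumption.

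**What to change.** Add ln(T1/2) as a response in the ANOVA of protocol 15.7 and SAP 11.4.2.1. Report the fed/fasted geometric mean ratio, its 90% CI and the number of complete pairs in Table 14.4.2.3, and in Table 14.4.2.8 if that table is produced. Extend both titles to name T1/2. Present the result as an estimate without acceptance limits, since the documents set none for T1/2. No separate rule for incomplete pairs is needed, because the fixed subject effect already restricts the contrast to complete pairs.

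The cost is one more response in an existing model and one table row. No sample, visit or derivation is added.
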